**eFigure 3. Signal to Noise Curves Across Range of Concentrations Tested for Four PD-L1 Antibodies in Tumor Cases**

**Figure 5. Schematic Layout of 15-Spot PD-L1 Reference TMA (A) and DAB Staining at Low Power Objective and QIF Staining at High Power Objective of 15-Spot reference PD-L1 IHC TMA for PD-L1 Antibodies (B)**

Figures (above): Data demonstrating Signal to Noise ratios and DAB staining with the 9A11 antibody compared with other widely used PD-L1 antibodies. Copied from supplementary materials from Gaule et al. JAMA Oncol. 2016.

Beyond PD-L1 IHC, other tissue biomarkers are exploratory. As above, meta-analyses have demonstrated the feasibility of assessing many of these exploratory immune

markers across cancer types. Our pathology group has published the methods, protocols, and data for many of these antibodies including PD-L1 as above and other antibodies to be used in this series of studies such as PD-L2. Antibodies for many other markers such as CD3 and CD8 are commercial and are currently used in the CLIA-certified hospital laboratory of Brigham and Women's Hospital for diagnostic purposes. As part of the validation assays in a CLIA-certified laboratory, identical cases were stained multiple times and under a variety of staining conditions and the results reviewed by two certified pathologists. A positive control sample (such as classical Hodgkin Lymphoma for PD-L1 expression; primary mediastinal large B-cell lymphoma for PD-L2 expression) and negative control sample (benign lymph node) is stained with each experimental tissue biopsy sample. The controls are reviewed by a certified pathologist at the time of review of the experimental sample.

The primary analysis will be performed on PD-L1 expression as a continuous PD-L1 metric (% positive tumor cells). Digital, quantitative scoring of stained tissue is performed using a slide scanning and analysis platform. Quantitative assessment of positive staining uses the commercially provided algorithm for cell identification and positive pixels counting within a pre-defined DAB (brown, chromogenic) channel. We have shown that this method of analysis shows good correlation with pathologists' scoring: Mino-Kenudson M et al., Clin Cancer Res. 2010 Mar 1;16(5):1561-71. PMID:20179225. [31]. We have also used this method to score PD-L1 expression in tumor cells: Green MR et al., Blood. 2010 Oct 28;116(17):3268-77. PMID: 20628145.[32] The quantitative scoring method is summarized in the following steps:

1. The pathologist takes 3-5 representative pictures for each case at 200x magnification
2. Tissue classification of the images is performed, where tumor and stroma are distinguishably labeled.
3. The pathologists perform "cell segmentation" where the whole image is segmented into individual cells based on hematoxylin as a nuclear stain
4. The pathologist trains the software to identify PD-L1 (+) and PD-L1 (-) cells on a cell-to-cell basis, based on expression and comparison to control tissues (tonsil).
5. Thresholds are established and then applied to the whole image by the pathologist.
6. A second pathologist checks the threshold, and either approves or disapproves it. In case of disapproval, the two pathologists reconcile between them.
7. Scoring for the positive cells is then performed in the tumor compartment.

Depending on tissue availability, other exploratory IHC analyses will be performed using semi quantitative scoring, although multiplex IF may be used as below to analyze multiple markers in tandem. Chen et al. [30] describes a semi-quantitative scoring method, which is in accordance with typical biomarker scoring in anatomic and surgical pathology [30]. Briefly, staining is scored according to intensity (0= no staining, 1= weak staining, 2= moderate staining, 3= strong staining), staining pattern (M= predominantly cell membrane; C= predominantly cell cytoplasm), and the percentage of cells showing positive staining (0-100%). The semi-quantitative scoring is performed for: 1) the neoplastic tumor cells and 2) the non-neoplastic infiltrating immune cells.

In the research setting, all cases are reviewed by two pathologists and any discordant results resolved by consensus review. Significantly discordant scoring results have been rare during case evaluations [30]. IHC scoring for markers (such as the PD-Ligands) that stain macrophages, dendritic cells, and other cells of heterogenous morphology will also be semi-quantitative and performed by a pathologist to capture 1) the percentage of neoplastic cells positive for biomarker expression, intensity of expression, and

membrane or cytoplasmic expression, and 2) the percentage of non-neoplastic cells (macrophages, dendritic cells, endothelial cells) positive for biomarker expression, intensity of expression, and membrane or cytoplasmic expression.

Scoring for PD-1+ (and other lymphoid markers) lymphocytes will be accomplished using a standard algorithm, developed for quantifying nuclear stains, but found to be applicable to quantifying membrane staining of cells with a very high N:C ratio, such as lymphocytes (Nuclear algorithm). The output is number of positive-staining cells per unit area (micron).

For image analysis:

IHC stained slides will be digitally scanned using the Aperio ScanScope XT (Leica Microsystems, Buffalo Grove, IL). The instrumentation is housed in the Tissue Microarray and

[figure not shown]
Imaging Core (TMI) facility of the Dana-Farber/ Harvard Cancer Center (DF-/HCC). This facility is located adjacent to the office of [name] in the Department of Pathology. All digital images are stored on servers owned by the TMI core facility and accessed via the internet using a password-protected log-in.

Digital images are viewed using ImageScope Software(version 10.0.35.1800; Leica) on standard PCs. Slides are digitally annotated by the pathologist (Dr. [name]) to identify the region of interest and analysis.

Quantitative analysis is performed using analytical software (for PD-Ligands). Intensity of staining is also captured automatically using the above algorithms and assigned a score (0, 1, 2, or 3) based upon the average optical density of the region or cells. All results are exported into an excel spreadsheet.

Individual scoring data will be compared to clinical parameters to determine if there is an association with outcome. Scores using a combination of biomarker data will also be considered.

Below, we provide a schematic of the workflow for the tissue-based biomarker analysis:

The semi-quantitative scoring for this study is in accordance with those published previously [30, 33] and will include scores for both the neoplastic and non-neoplastic cells within the tumor microenvironment. Data derived from pathologist visual scoring (semi-quantitative, but with increased specificity for delineating neoplastic and non-neoplastic cells) and pathologist-assisted, automated scoring (quantitative, but without accurately delineating neoplastic and non-neoplastic cells) for each marker of interest will be assessed for its clinical value. As necessary, the data from combinations of markers will also be considered.

All IHC staining will be performed in the Center for Immuno-Oncology Pathology Core at Dana-Farber/Harvard Cancer Center Specialized Histopathology Core which is a designated Cancer Immune Monitoring and Analysis Center (CIMAC). Standard EnVision two-step (indirect) staining method will be utilized. Four-micrometer-thick sections will be cut, deparaffinized, rehydrated and subjected to heat mediated antigen retrieval in citrate buffer (pH 6) (Invitrogen) by steaming for 30 minutes. After cooling, tissue sections will be incubated with peroxidase block (DAKO, Carpinteria, CA) for five minutes, then serum free protein block (DAKO) for 20 minutes. Slides will be incubated at room temperature for one hour with a primary antibody. Antibodies will be diluted in Da Vinci Green Diluent (Biocare Medical, Concord, CA). Envision™ anti-mouse HRP-labeled polymer (DAKO) will be applied to the sections for 30 minutes, followed by

visualization by using the chromogen 3, 3-diaminobenzidine (DAKO). All the sections will then be counterstained with haematoxylin, dehydrated, mounted and coverslipped. Positive and negative controls shall be included in each staining. Known positive stained Hodgkin lymphoma (CD274) will be used as external control (separate slides). Stained slides will be stored at room temperature.

For multiplex immunofluorescence, we use the Opal™ Multiplex Immunohistochemistry kit, which is a practical workflow for simultaneous detection of up to 6 tissue biomarkers plus nuclear counterstain, within a single image. Antibodies for simultaneous IHC may be selected based on performance, rather than species. This kit provides the tools to interrogate multiple pathways while retaining context provided by tissue images.

Methods: Step 1. Overnight baked FFPE slides are de-paraffinized and then placed in AR6 solution (PerkinElmer) for 15min using a microwave. AR6 solution was developed for use in the multicolor immunohistochemistry protocol in microwave treatment, and provides antigen retrieval for FFPE tissues, quenches endogenous peroxidase, and removes antibodies after epitopes have been labeled with Opal dyes. Step 2. After the antigen retrieval step, the slides are cooled in room temperature for 20 min and then washed with distilled water and then with Tris buffer. Step 3. Afterwards, the first antibody for Protein 1 (example: PD1) is applied for 40 minutes. Step 4. HRP-linked secondary antibody (Dako Envision kit) is applied for 30 minutes. Step 5. After a few washes in Tris buffer (3x2minutes) the 1st Opal Fluorophore is applied (1:50, diluted in Amplification Diluent) for 5 minutes. Step 6. The slides are washed in Tris buffer and placed in pre-heated AR6 solution for 15 minutes using a microwave. Step 7. After this, the first antibody for Protein 2 (example: CD30) is applied and all the Steps 2-6 are repeated. Currently, using the Opal-7 Color Immunohistochemistry Kit, we can stain for 6 different proteins and Dapi.

To accurately visualize, analyze and quantify the different biomarkers in tissue sections, we use InForm®, which is an automated image analysis software package (PerkinElmer). inForm enables accurate per cell quantification of specific biomarkers defined within multiple tissue types including tumor and stroma and the phenotyping of immune cells and other cells in situ in solid tissue. It also enables the quantitation of weakly expressing and overlapping biomarkers within cells, nuclei and membranes, which cannot be identified by eye. This sensitive approach provides researchers with the confidence to discover indicators of disease and uncover relationships between biomarkers, improving results reliability.

#### Assay performance

As above, validation has been performed on retrospective data sets. Protocols have been optimized and standardized to minimize staining variance. Positive control and negative controls were used and stained separately with each batch of slides for PD-L1 staining. The IHC staining of PD-L1 has been performed in two different labs by three different technicians on whole tissue sections of Hodgkin lymphomas, melanomas, lung cancers and renal cell carcinomas. Three readers were involved, confirming the good reproducibility of the assay. Consistency of automated PD-L1 scoring has been confirmed on 10 colorectal and 7 lung cancer cases.

#### Laboratory information

The IHC and IF staining will be conducted in a research laboratory with GLP standard under the direction of [name]. [name] is the overall supervisor of the lab, and is a hematopathologist at the Brigham and Women's hospital with prior expertise evaluating PD1, PDL1 and other immunologic markers in paraffin embedded tumor

samples [30]. PD-L1 IHC and the multiplex IF panel examining CD8+ T-cell infiltration will be performed under the auspices of the CIMAC. Other exploratory IF panels, specifically those exploring hypothesized mechanisms of resistance (CTLA-4, MHC-1, MHC-2, Lag-3, B2M, Na channel) will be performed in the same laboratory but are not currently planned to be incorporated as core CIMAC assays.

Laboratory methods for evaluating serum and PBMCs:

Peripheral blood mononuclear cells (PBMC's) will be analyzed using CyTOF via the CIMAC. DFCI CIMAC reference document is in development and validation data will be sent to NCI under the CIMAC vetting process. Existing analytical validation data is available from Klensteuber et al.: Standardization and Quality Control for High-Dimensional Mass Cytometry Studies of Human Samples Cytometry A. 2016 Oct; 89(10): 903–913. As an example of the capabilities of the CyTOF assay in general to be offered through the CIMAC, please see attached reference document provided by Human Immune Monitoring Center at Mt. Sinai. As described in this reference document, "CyTOF offers single-cell level detection of 40+ markers with inter-channel cross talk levels <4% and very low background signals (<2 integrated dual counts ion per cell). The accuracy of individual antibodies is expected to be comparable to the analogous antibody clones used for conventional flow cytometry, and the accuracy of defined cell population identification is comparable to, if not better than flow cytometry."

Cytokine / serum analysis:

Cytokines will be analyzed using Olink via the CIMAC (Mt. Sinai). Please see attached reference document provided by Human Immune Monitoring Center at Mt. Sinai. As described in this reference document, O-link is "a 92-parameter targeted soluble factor immunoassay" that allows for "quantification and correlation of multiplexed cytokine levels." Precision, analytical sensitivity, and analytical specificity are described in more detail in this document.

#### A. Facilities & personnel

PD-L1 IHC and multiplex IF including CD8+ T-cell analysis will be performed in the laboratory of [name] at the DFCI as part of the DFCI CIMAC. Other multiplex IF panels described above examining mechanisms of resistance will be performed in the same laboratory, but are not currently CIMAC assays.

CyTOF will be performed via the DFCI CIMAC under the direction of [name].

Olink will be performed via the Mt. Sinai CIMAC - Human Monitoring Core / [name] MD PhD, Director.

## IV. Statistical Considerstions

### A. Endpoints

1. Primary
  - a) PD-L1 positivity
  - b) Percent of circulating, activated CD8+/HLA-DR+/Ki-67+ T-cells
2. Secondary
  - a) PD-L1 positive cases

- b) Infiltration of lymphocytes per high powered field
- c) Exploratory analyses of expression levels of various serum cytokine and tumor immune biomarkers

B. Case selection and Sample Size

All consenting cases with adequate biospecimen available from the Z1D subarm.

Sample size estimate: 44 patients for tissue analyses, 37 patients for blood analyses

C. Analysis plan:

Regarding the primary endpoint of PD-L1 expression in tumor tissue, an unpaired t test will be used to compare the percent positive tumor cells in responders vs. non-responders. Responders will be determined using the primary endpoint of the trial – objective tumor response. Using the data provided in the supplementary appendix to Le et al. as a basis for the power calculations (Le DT, Uram JN, Wang H, et al. PD-1 blockade in tumors with mismatch-repair deficiency. N Engl J Med 2015;372:2509-20) it is assumed that PD-L1 expression, measured as a percentage of positive cells, will have a mean percentage of roughly 20% and a standard deviation of about 10%. Using these figures and assuming also that roughly 24% of all patients in this subarm will be responders, with approximately 44 patients with tissue available (roughly 11 responders and 33 non-responders) there is at least 80% power to detect a mean difference of 10% (e.g., 29% versus 19%) in PD-L1 expression between responders and non-responders using a two-sided 0.05 level t-test. The 24% figure used for the calculations was chosen based on the results of this arm recently presented at SITC.

Given the small sample size of this subarm, a categorical analysis to correlate objective response with PD-L1 positivity (for example via Fisher's exact test using a 5% cutpoint for PD-L1 positivity) will not have meaningful power, hence the proposed analyses will be done on the continuous PD-L1 metric and any categorical analyses will be considered exploratory. Following the logic of the power analyses above, there is 80% power to detect a 1.00 standard deviation difference in the means of any quantitative biomarker between responders and non-responders (assuming the overall response rate above) using a two-sided 0.05 level t-test.

The primary objective is to examine the association between a single biomarker (PD-L1 expression) and response. Thus, no statistical adjustments are planned for this analysis. Other planned IF and IHC testing is exploratory and largely based on mechanistic hypotheses (e.g. exploring for treatment resistance as a consequence of defects in the MHC I or MHC II expression and antigen presentation pathways). Therefore, exploratory analyses will be descriptive in nature with no planned adjustment for multiple testing.

When genomics data are available from the NCI MATCH study we may perform exploratory analyses to examine associations with protein expression across the markers tested. Specifically, there are immediate plans to attempt to look at numbers of MOIs based on the NCI MATCH assay as a proxy for high mutational burden for arm Z1D and correlate this with response. We will correlate this measure with our primary endpoint of PD-L1 expression as well as with our other exploratory endpoints.

The primary endpoint of studies to be conducted on peripheral blood will evaluate changes in percentage of circulating CD8+/HLA-DR+/Ki-67+ T cells and response. We will compare the change in percentage of this cell population between responder and non-responder patients. To give a sense of power for studies to be done on paired tissue and blood samples (baseline versus progression), and blood samples (paired within patient comparing baseline vs progression) for analyses of various quantitative biomarkers being proposed here, differences will be taken for all measures and the hypotheses is that biomarkers will change (increase or decrease) post therapy. PD-L1 expression on tumor cells, infiltrating and circulating T-cell populations, myeloid derived suppressor cells, and immunologic cytokines and other immunologic markers. Assuming that within this cohort we will obtain paired samples on conservatively 40 patients, using a two-sided 0.05 level paired t-test there is at least 80% power to detect a 0.46 SD change in mean of a quantitative correlative parameter using a two-sided test with 5% type I error. Quantitative measure will be transformed to attain normality or appropriate non-parametric tests will be conducted. With this level of consent for these studies in this cohort there is sufficient power for meaningful analyses. Power for these tests will be further improved if a greater percentage of the cohort of 47 patients consent and provide post-baseline (progression) samples for analysis.

D. Rationale for the sample size estimate:

As described above, assuming that roughly 24% of all patients in this subarm will be responders, with 44 patients (expected distribution to be roughly 11 responders and 33 non-responders) there is at least 80% power to detect a mean difference of 10% (e.g., 29% versus 19%) in PD-L1 expression between responders and non-responders using a two-sided 0.05 level t-test.

For the blood studies, assuming approximately 40 patients have usable specimens pre and post treatment, using a two-sided 0.05 level paired t-test there is at least 80% power to detect a 0.46 SD change in mean of a quantitative correlative parameter using a two-sided test with 5% type I error.

We propose to evaluate associations with PD-L1 expression measured as a continuous metric of positivity (as described above) as opposed to a single cutoff. Exploratory analyses will assess specific cutpoints of PD-L1 positivity (e.g. 1%, 5%, 10%, etc.) as potential biomarkers, as these cutpoints have been described previously in the literature. To our knowledge there are unfortunately no on-treatment pathologic specimens available and therefore magnitude of change on treatment cannot be assessed. As mentioned in the above statistical analysis plan, assuming that within this cohort we will obtain paired samples on conservatively 40 patients that yield evaluable data for our flow-cytometric biomarkers, using a two-sided 0.05 level paired t-test there is at least 80% power to detect a 0.46 SD change in mean of a quantitative correlative parameter using a two-sided test with 5% type I error. Quantitative measures will be transformed to attain normality or appropriate non-parametric tests will be conducted as appropriate. We will also compare changes between responder and non-responder groups for the purpose of our analyses.

E. Statistical considerations for secondary objectives (if applicable)

Our secondary objectives for testing multiple biomarkers in tissue and serum are exploratory. However, these objectives are based on strong biologic rationale

and may also identify future targets for combinations with PD-1 inhibitors in patients with mismatch repair deficiency or other tumors.

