## II. Objectives

### A. Primary objectives:

1. Studies in tissue: The primary objective of this study will be to determine associations between PD-L1 expression (quantitatively determined as a continuous variable) in tumor tissue at baseline and an objective response to protocol treatment.
2. Peripheral blood studies: To determine association between changes in percentages of circulating activated T-cells, specifically CD8+/HLA-DR+/Ki-67+ T cells and an objective response to protocol treatment.

B. Exploratory studies

1. To associate levels of tumor infiltrating CD8+ T-cells, and PD-L1 expression defined categorically, and also in specific cell populations such as tumor cells and tumor infiltrating lymphocytes with response
2. As tissue allows, to explore correlations between response and multiple immunologic biomarkers including PD-1, CTLA-4, MHC-1, MHC-2, Lag-3, B2M, Na channel and other exploratory multiplex IF to determine expression levels of these biomarkers in components of the tumor microenvironment and in relation to each other
3. To evaluate mechanisms of resistance by comparing immunologic markers in sequential biopsies and biopsies taken at progression if available
4. To explore correlations between PD-L1 expression and CD8 + T-cell tumor infiltration with overall tumor mutational burden as determined by whole-exome and targeted sequencing to be performed through the parent NCI MATCH study
5. To explore associations between changes in a panel of circulating immune populations and immunologic cytokines with response Methodology

III. **Methodology**

Summary:

Correlative science will involve immune evaluation of archival tissue, serum and PBMCs obtained from multiple time points. PD-L1 expression and CD8+ T-cell infiltration will be evaluated on cut FFPE slides as below to correlate with response. We will also examine changes in these biomarkers over time when sequential biopsy specimens are available. Additional tissue, when available will be used for multiplexed IF and assayed for other immunologic markers as described in detail below. CyTOF will primarily examine changes in circulating activated T-cells over the course of therapy as a predictor of response but will also explore other immune subsets and cytokines.

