Patients enrolled on MATCH Z1D have loss of MLH1 or MSH2 as determined by IHC performed at the Central Pathologic lab for the NCI MATCH study. Other MSI testing is currently outside of the scope of the current correlative proposal, although additional testing can be considered if adequate tissue is remaining.

No patient identifiers will be provided to investigators with the samples. The trial-specific patient ID will be replaced with a unique randomized number and specimens will be labeled with a barcode not related to any PHI. The following entities have access to the key: the ECOG-ACRIN biobank, the ECOG-ACRIN Operations Office, and the MATCH statisticians.

Prioritization of tissue:

Formalin fixed-paraffin embedded (FFPE) tumor slides will be prepared and a slide H&E stained from all tumor samples. Immunohistochemical (IHC) and multiplex immunofluorescent (IF) staining will be performed on FFPE tumor slides using some or all of the following antibodies/assays. Since there may not be sufficient tissue to perform all the assays in every sample we have prioritized the assays. In the order of priority based on the amount of tissue available, the assays we will perform include:

- IHC to determine intratumoral PD-L1 (CD274) expression

[figure not shown]

- IF to determine tumor infiltrating lymphocytes (TILs) using CD8 expression
- Exploratory multiplex IF and IHC to evaluate response and distribution of PD-L1 staining in conjunction with other markers such as tumor infiltrating lymphocytes and PD-1 expression and, and other immunologic markers will be performed including CD3, CD8, CTLA-4, MHC-1, MHC-2, Lag-3, B2M, Na channel, (these will only be performed if there is sufficient tissue)

Materials and methods for studies in tissue:

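### Appendix V states 80% power at 1.00 SD for any quantitative biomarker, but the figure holds only for markers measured in all 44 tissue cases (11 responders, 33 non-responders)

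*Protocol*

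**What the plan says.** Appendix V, section IV.C (Analysis plan), first derives the power for PD-L1 expression. It assumes that "roughly 24% of all patients in this subarm will be responders" and works "with approximately 44 patients with tissue available (roughly 11 responders and 33 non-responders"), with a mean of about 20%, an SD of about 10% and a difference of 10 percentage points, "using a two-sided 0.05 level t-test".

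The next paragraph generalises. "Following the logic of the power analyses above", it states that "there is 80% power to detect a 1.00 standard deviation difference in the means of any quantitative biomarker" between the two response groups. The one condition it repeats is the overall response rate. It names no number of evaluable cases and does not restrict the markers.

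Three other places bear on the number of cases:

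- Section IV.B estimates 44 patients for tissue analyses and 37 for blood analyses.
- Section III (Prioritization of tissue) says: "Since there may not be sufficient tissue to perform all the assays in every sample we have prioritized the assays". PD-L1 IHC comes first, CD8 immunofluorescence second, and the exploratory multiplex and IHC panel last. Of that panel it says "these will only be performed if there is sufficient tissue".
- Section II.B, item 2, opens: "As tissue allows, to explore correlations between response and multiple immunologic biomarkers".

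**The concern.** A power statement for a two-group comparison is tied to the two group sizes. Here the sizes used for one assay, PD-L1 IHC, are applied to all quantitative markers, although the same appendix gives a smaller number for blood and foresees that tissue may run out for the lower tiers.

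At stake is how a null result is read. The primary blood endpoint compares the change in circulating CD8+/HLA-DR+/Ki-67+ T cells between responders and non-responders. The only blood-specific power in the appendix (0.46 SD with 40 pairs) is for a within-patient paired test, which is a different comparison. The 1.00 SD sentence is therefore the only power figure available for the responder comparison in blood. The antigen-presentation markers (MHC-1, MHC-2), for which section IV.C names a resistance hypothesis, sit in the last tissue tier. In either setting, failure to find a true 1 SD difference could be read against 80% power that the evaluable number does not deliver.

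**Working it through.** **Inputs from Appendix V.** Unpaired t-test, two-sided alpha 0.05; true difference d = 1.00 SD (10 points on an SD of 10); response rate about 24%; 44 tissue cases split 11/33; 37 blood patients; 40 paired samples in the blood power text.

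**Formula.** With group sizes n1 and n2, df = n1 + n2 − 2 and noncentrality δ = d × √[n1·n2/(n1 + n2)]. Power is the probability that a noncentral t variable with these parameters exceeds the 97.5% point of the central t (the opposite tail is negligible). The detectable difference is the d at which power equals 80%.

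**Step 1: the plan's own figure.** 11 × 33/44 = 8.25, so δ = √8.25 = 2.872; df = 42, critical value 2.018. Power = 80.1%, detectable difference 0.998 SD. The stated 80% at 1.00 SD is reproduced.

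**Step 2: reserve at 44.** 24% of 44 is 10.56, rounded in the plan to 11. Using 10.56/33.44 without rounding gives 79.0%. Losing a single responder (10/33) gives 77.2%.

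**Step 3: the document's blood number.** 24% of 37 is 8.9, so about 9/28. 9 × 28/37 = 6.811, δ = 2.610; df = 35, critical value 2.030. Power = 71.8%, detectable difference 1.10 SD. If the 40 paired samples in the blood power text are used instead, 24% is 9.6, so about 10/30. 10 × 30/40 = 7.5, δ = 2.739, and power is 76.1% with a detectable difference of 1.05 SD. Neither number reaches 80% at 1.00 SD.

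**Step 4: lower-priority tissue assays.** No expected number per assay is given, so the rows below 44 are assumed for illustration. All keep the 1:3 split.

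| Evaluable cases | Split | Power at 1.00 SD | Detectable at 80% |
|---|---|---|---|
| 44 | 11/33 | 80.1% | 1.00 SD |
| 40 | 10/30 | 76.1% | 1.05 SD |
| 36 | 9/27 | 71.4% | 1.11 SD |
| 28 | 7/21 | 59.7% | 1.27 SD |

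**Step 5: small losses.** The effect of losing a few cases depends on which cases are lost. At 42 cases, power is 78.2% with the 1:3 split held, 79.4% if both lost cases are non-responders (11/31), and 76.8% at 10/32. Small losses therefore cost little unless they fall on responders.

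**The case against.** The 80% figure is right on its own inputs, and the sentence refers back to a calculation that names 44 patients, so the condition may be thought inherited. Forty-four is described as the number for tissue analyses in general, not for PD-L1 alone. The appendix elsewhere gives the cohort as 47, so 44 may already allow for some cases without adequate tissue. Submission of an archival block or 20 unstained slides, if available, is marked mandatory in the study parameters, and multiplex staining reads up to six markers in one image, so large losses are not a given. The other IF and IHC work is exploratory and descriptive, and any hypothesis-generating result is to be validated in later studies. Finally, the sentence stands in a passage about tissue and might be read as not covering blood.

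Much of this stands. A reader might infer from the priority list that the lower-tier assays will not be run on every case, so that the stated power does not exist for them. The documents do not support that: they say tissue may fall short, give no expected shortfall, and leave open that all 44 cases suffice. Nor is it an arithmetic error.

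What does not remove the point is the wording. The sentence says any quantitative biomarker and repeats only the response rate as a condition. The blood number of 37 is the document's own and needs no assumption about tissue. If the sentence is meant for tissue only, it should say so; the primary blood comparison between responders and non-responders then has no power statement at all. Exploratory status lowers the stakes for the tissue markers but does not make an unqualified figure accurate.

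**Conclusion.** The concern holds as a matter of scope. The statement of 80% power at 1.00 SD is correct for markers measured in all 44 tissue cases split 11/33 (80.1%), and too wide as written.

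The firm part is blood: at the planned 37 patients, power is about 72% and the detectable difference about 1.10 SD. This rests on the 24% response rate applying equally to patients with blood samples.

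The conditional part is tissue. Forty-four is a ceiling for the lower-priority assays, and the loss below it is unknown; the table shows what assumed numbers from 40 down to 28 would mean. The PD-L1 analysis is not affected, because it has first call on tissue. No confirmatory tissue conclusion is at risk.

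**What to change.** In Appendix V, section IV.C:

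1. Limit the sentence to quantitative biomarkers evaluable in all 44 tissue cases (about 11 responders and 33 non-responders).
2. Add that, for the responder comparison in blood at the planned 37 patients, the difference detectable with 80% power is about 1.10 SD.
3. For the lower-priority tissue assays, give the detectable difference at a few smaller evaluable numbers (for example 1.05 SD at 40, 1.11 SD at 36, 1.27 SD at 28), marked as illustrations.

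The cost is one or two sentences and, if wanted, a small table. No patients, tissue or assays are added. The price is that the stated sensitivity for these markers becomes less favourable.
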